4.10 Multicenter trials

Study center may have an impact on the study outcomes and therefore will be used as a covariate in the primary and secondary efficacy analyses.

4.11 Primary Endpoint Analysis

The primary population of all efficacy analyses will be the ITT Analysis Set. The change from baseline in WOMAC pain subscale score will be analyzed using an ANCOVA model with main effect treatment and covariates study center and baseline score. The primary timepoint for analysis will be week 17. Since an interim analysis is to be performed, the final analysis will be conducted between each of the three treatment arms and placebo using a simple combination test (1/2 weight on interim Z and 1/2 weight on final Z) in order to maintain the overall specified alpha level. Further, p-values will be adjusted (and compared to 0.05) using a step-down Dunnett testing method for comparison of the three active doses with placebo.

The step-down testing method will first apply Dunnett adjustment for three comparisons (0.3 mg/kg, 1.0 mg/kg, and 2.0 mg/kg LEVI-04) with placebo. If the lowest adjusted p-value is non-

LEVI-04-21-02 Statistical Analysis Plan	Version: Final 3.0
Date: 18-Mar-2024	Page 20 of 34

significant (>0.05), then all three comparisons will be considered non-significantly different from placebo. If the lowest adjusted p-value is significant (≤ 0.05), then the associated LEVI-04 dose level will be considered significantly different from placebo. The testing will continue by applying a Dunnett adjustment for two comparisons (the remaining two LEVI-04 dose levels) with placebo. If the lowest adjusted p-value from the two comparison Dunnett adjustment is non-significant, then the remaining two dose levels will be considered non-significantly different from placebo. If the lowest adjusted p-value from the two comparison Dunnett adjustment is significant, then the associated LEVI-04 dose level will also be considered significantly different from placebo. Testing will continue by comparing the unadjusted p-value to 0.05 for the last LEVI-04 dose level versus placebo. This procedure preserves the global type 1 error. Adjusted p-values from the stepdown Dunnett may not be smaller than the smallest adjusted p-value reported from the previous step. If the smallest Dunnett adjusted p-value from one of the steps is smaller than the previous step's adjusted p-value, then the p-value from the current step will be set to the previous step's adjusted p-value. Dunnett adjustments to the p-values will be calculated using the SAS® PROBMC function. In the first step, for each of the three comparisons, the Z from the associated combination test will be utilized by the PROBMC function as follows to calculate the adjusted pvalue:

$$adj_p3 = 1 - PROBMC("DUNNETT2", max_abs_z, ., ., 3, lam1, lam2, lam3);$$

where,

 $max_abs_z = Maximum of the absolute value of all three combination Z-statistics$

n0 = n01 + n02: placebo sample size at the end of the study

n1 = n11 + n12: LEVI-04 0.3 mg/kg sample size at the end of the study

n2 = n21 + n22: LEVI-04 1.0 mg/kg sample size at the end of the study

n3 = n31 + n32: LEVI-04 2.0 mg/kg sample size at the end of the study

where nij is the sample size of the ith group (i=0,1,2,3) at the interim (j=1) and post interim (j=2) periods.

$$lam1_{-1} = \sqrt{\frac{n11}{n11 + n01}}$$

$$lam2_{-1} = \sqrt{\frac{n21}{n21 + n01}}$$

$$lam3_{-1} = \sqrt{\frac{n31}{n31 + n01}}$$

$$lam1_{-2} = \sqrt{\frac{n12}{n12 + n02}}$$

LEVI-04-21-02 Statistical Analysis Plan	Version: Final 3.0
Date: 18-Mar-2024	Page 21 of 34

$$lam2_2 = \sqrt{\frac{n22}{n22 + n02}}$$

$$lam3_2 = \sqrt{\frac{n32}{n32 + n02}}$$

Correlations among the interim Z-statistics

Correlations among the post-interim Z-statistics

Correlations among the (final) combined Z-statistics

$$\rho 12 = (\rho 12_1 + \rho 12_2)/2$$

$$\rho$$
13=(ρ 13_1+ ρ 13_2)/2

$$\rho$$
23=(ρ 23_1+ ρ 23_2)/2

$$lam1 = \sqrt{\frac{\rho 12 * \rho 13}{\rho 23}}$$

$$lam2 = \sqrt{\frac{\rho 12 * \rho 23}{\rho 13}}$$

$$lam3 = \sqrt{\frac{\rho 13 * \rho 23}{\rho 12}}$$

LEVI-04-21-02 Statistical Analysis Plan	Version: Final 3.0
Date: 18-Mar-2024	Page 22 of 34

adj_p3 = Dunnett adjusted p-value for the maximum absolute value of all three combination z-statistics.

The above procedure will be similarly applied to the remaining dose groups using PROBMC:

adj_p2 = 1 - PROBMC("DUNNETT2", max_abs_z, . , . ,2,lam_i,lam_j);

where:

LEVI-04-21-02 Statistical Analysis Plan	Version: Final 3.0
Date: 18-Mar-2024	Page 23 of 34

max_abs_z: Maximum of the absolute value of the remaining two combination Z-statistics lam_i,lam_j: the lambdas for the remaining groups

In the third step, the remaining adjusted p-value will be adj_p1=p1, i.e., no adjustment. Following the calculation of the p-value adjustment, the following process will ensure monotonicity of the adjusted p-values:

```
adj_p3=adj_p3;
adj_p2=max(adj_p3,adj_p2);
adj_p1=max(adj_p2,adj_p1);
```

The WOMAC pain subscale score will be tabulated per time point (visit) and treatment group, along with the absolute change from baseline where baseline is defined as the latest assessment prior to first treatment administration.

For the treatment effect testing of IMP versus placebo, the null and the alternative hypothesis will be:

```
H0: Mean (Placebo) = Mean (IMP)H1: Mean (Placebo) ≠ Mean (IMP)
```

If the null hypothesis is rejected, the alternative hypothesis will be accepted, and it will be concluded that the treatment effect of IMP differs from placebo.

The The SAS® Mixed procedure will be utilized as follows.

```
proc mixed;
class site trt;
model val = trt site base;
run;

where:
val = dependent variable (eg. change from baseline in WOMAC pain subscale score)
site = Investigational Site,
trt = Treatment (Arms A, B, C, D),
base = Baseline WOMAC pain subscale score
```

LEVI-04-21-02 Statistical Analysis Plan	Version: Final 3.0
Date: 18-Mar-2024	Page 24 of 34

To assess the robustness of the primary results, sensitivity analysis will be performed with modification of participant population (mITT and PP Analysis Sets) using observed data only. Further investigation of the robustness of the primary results (in particular, the influence of time and covariates) may be performed, if deemed necessary.

4.12 Secondary Endpoint Analyses

Secondary endpoints will be analyzed based on the ITT Analysis Set using observed data only. Continuous or ordinal categorical endpoints will be analyzed using the same model as specified for the primary endpoint at each visit, where applicable, unless otherwise stated. Dichotomized secondary endpoints such as the Proportion of participants achieving 30% and 50% reduction in WOMAC Pain subscale scores at week 5 and week 17, will be analyzed using a logistic regression model, with PROC GENMOD, with main effect treatment and covariates study center and baseline WOMAC pain subscale score, and where the link function is logit, and the distribution is binomial. In addition to the ITT Analysis Set, WOMAC physical function subscale score, Staircase Evoked Pain Procedure (StEPP) Pain Intensity, WOMAC stiffness subscale score, PGA, and the Numeric Rating Scale (NRS) pain score will be summarized by the mITT and PP Analysis Sets.

NRS pain score is collected daily. Weekly post-baseline average daily scores will calculated for all weeks through Week 20 regardless of whether or not there was a scheduled visit at that week. Weeks will be calculated according to actual study days. Since daily NRS pain is reported in the evenings, it will be assumed that the Day 1 assessment is collected after dosing. Therefore, Week 1 will be calculated from NRS scores collected on Days 1 through 7, Week 2 from Days 8 through 14, etc. Baseline average daily pain score will be calculated as the average of scores collected on the seven days prior to first dose of study drug (Day 1). Missing daily pain scores will not be imputed. Weekly post-baseline average daily scores will be calculated if at least four of the seven scores are non-missing. The denominator for determining the weekly score will only include days with a non-missing score.

The area under the curve for average daily NRS pain will be calculated using the linear trapezoidal method from Day 1 through Week 20 (Day 141) or the last non-missing daily NRS pain score, whichever comes first. Missing daily pain scores will not be imputed. The area under the curve for the average daily NRS pain will be analyzed using the same model as the primary endpoint.

The average amount of daily rescue medication usage while on study treatment and the proportion of days of rescue medication use while on study treatment will be calculated based on the diary, which captures daily use of rescue medication. The average amount of rescue medication used per day while on study treatment will be calculated as the total number of tablets taken on or after the first dose of study drug divided by the total number of days with known medication usage [i.e.,

LEVI-04-21-02 Statistical Analysis Plan	Version: Final 3.0
Date: 18-Mar-2024	Page 25 of 34

specified as no usage (0 tablets) or the number of tablets taken provided]. Similarly, the proportion of days of rescue medication use will be calculated as the number days rescue medication was used divided by the total number of days with known medication usage (i.e., usage specified as "yes" or "no"). These two rescue medication endpoints will be analyzed using an ANCOVA with main effect treatment and covariates sex, baseline BMI, baseline target knee WOMAC pain subscale score, and baseline OA category (unilateral, bilateral). Bilateral OA participants have both knees with a Kellgren Lawrence (KL) grade ≥ 2 and unilateral OA participants have only one knee with a KL grade ≥ 2 .

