5.4.1 Process for Early Termination

In case a participant discontinues trial prior to completion, the Investigator must make every effort to schedule and complete an EOT visit 4 weeks +/- 3 days following last administration of IMP and a Follow-up Safety Phone Visit (minimum 12 weeks following last dose of IMP). The assessments and procedures to be completed at EOT visit for participants that have withdrawn from study prior to completion and received at least one dose IMP, are as listed for FU/EOT Visit 11 and Safety Follow-up Phone Visit 12. It should be assessed if a TEAE was the primary reason for withdrawal. In this case, the TEAE must be documented, reported, and followed as described in Section 9.1.1.

Reason for participant withdrawal from the study and the date of discontinuation will be recorded on the electronic Case Report Form (eCRF).

A participant will be considered lost to follow-up if he or she fails to return for any scheduled visit and is unable to be contacted by study site staff. Should the participant continue to be unreachable 6 months after IMP administration, he or she will be considered to have withdrawn from the study with a primary reason of lost to follow-up.

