8.5 Follow-up Period

8.5.1 Visit 11 (Week 20, Day 141 ±3 days): Follow-up Visit/End of Trial Visit

The assessments and procedures as described below apply to Visit 11 and EOT visit for participants that have discontinued trial prior to completion of Visit 10 procedures and assessments. For participants that have discontinued trial early, the EOT visit should be attempted completed within 4 weeks (+/- 3 days) following last received IMP administration.

- Review of 48-hour washout of Rescue Medication prior to visit.
- Assessment of changes in concomitant medication.
- Review of new potential AEs and follow-up on ongoing AEs
- Survey of Autonomic symptoms
- BCTQ
- Vital signs
- Weight measurement
- BMI calculated automatically in EDC
- Physical exam (including Musculoskeletal Examination)
- Blood sample for:
 - o Safety Hematology and Chemistry
 - o PK blood sample to be collected
 - ADA to be collected
 - o PD biomarker sample to be collected
- Urine dipstick hCG for Women of Childbearing Potential
- Final accountability of Rescue Medication
- Radiographs bilateral knee-, shoulder- and hip joints
- MRI Target Knee

Version Version 3.0_07FEB2023

8.5.2 Visit 12 (Week 30, Day 212 ±7 days): Follow-up (FU) Safety Phone Visit

Site will contact the study participant per phone to complete following assessments:

- Assessment of changes in concomitant medication
- Review potential new AEs and follow-up on ongoing AEs. See Section 9.4 for description on procedure for AEs ongoing at Visit 12.

9 Assessment of Safety

The safety profile of the IMP will be assessed through the recording, reporting, and analysis of baseline medical conditions, AEs, physical examination findings including vital signs and laboratory tests and procedures, including ECGs in Screening and prior to each dosing. Safety assessments to be performed as per the:

- Interim Analyses Charter
- Independent Adjudication Committee for Adverse Events relating to Joint Safety Charter
- Medical Monitoring Plan
- Pharmacovigilance Plan
- Safety Monitoring Committee Charter

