4. STATISTICAL METHODOLOGY

4.1 General Principles

All collected study data will be presented in listings. All derivations and statistical analyses will be performed using SAS® software Version 9.4. Prior and concomitant medications will be coded using the current version of the World Health Organization (WHO) Drug Dictionary available at the start of the study and will be used for the duration of the study even if a newer version of the dictionary is released. Similarly, adverse events (AEs) and medical history will be coded using the current version of the Medical Dictionary for Regulatory Activities (MedDRA) available at the start of the study and will be used for the duration of the study.

Unless stated otherwise, descriptive summaries for continuous variables will include n (number of participants with non-missing results), mean, standard deviation (SD), median, minimum, and

LEVI-04-21-02 Statistical Analysis Plan	Version: Final 3.0
Date: 18-Mar-2024	Page 14 of 34

maximum. For categorical variables, n and percent will be provided. Percentages will be calculated out of the number of participants in the given population with a non-missing result.

Nominal outcome summaries, presented by collection day and/or by time point, will be based on scheduled assessments as planned in the protocol. Unscheduled assessments will be presented in listings and will not be included in the analyses except for determination of Baseline as described in Section 5.1. All other visit and time point collections will be as recorded on the electronic case report forms (eCRFs).

WOMAC subscale scores will be standardized to a range of 0 to 10. Imputation of missing WOMAC pain subscale scores described in Section 4.9 will be based on the original score range. Standardization will occur after imputation at the time of analysis. Listings will present the original scores.

The primary analysis will be conducted once data collection associated with this analysis has been completed. That is, no additional data will be collected that would affect the results of the primary analysis despite the study being ongoing.

Unless otherwise stated, hypothesis testing will be two-sided with an alpha level of 0.05.

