4.9 Missing data

The WOMAC osteoarthritis index is a self-administered questionnaire consisting of 24 items divided into three subscales: pain (5 items), stiffness (2 items), and physical function (17 items). Scores for the subscales are based on the sum of the responses (each ranging from 0, no symptoms, to 10, worst imaginable) within the subscale. If participants fail to complete all questions, then missing responses will be imputed as the mean of the non-missing responses within the same subscale provided that:

LEVI-04-21-02 Statistical Analysis Plan	Version: Final 3.0
Date: 18-Mar-2024	Page 18 of 34

- Pain Subscale: no more than one response is missing,
- Stiffness Subscale: no more than one response is missing,
- Function Subscale: no more than three responses are missing.

If the number of missing responses for a given subscale meets the specified criterion, then the overall score for the subscale is calculated according to the non-missing and imputed responses and considered as an observed response. If more than the specified number of responses is missing, the subscale is considered invalid and the subscale score is considered missing. All non-missing responses will be presented in listings regardless of the number of missing responses.

Missing data for the primary endpoint (WOMAC pain subscale score) will be imputed using multiple imputations (MI) methodology. All missing visits data will be imputed using all prior visits data as well as treatment. Data that is missing at random will be imputed using the randomized treatment assignment, whereas data that is missing due to treatment (adverse event, lack of efficacy) will be imputed using placebo as the treatment. For the MI model, 100 imputations will be generated using PROC MI of SAS®. Fully conditional specification (FCS) model using the regression method will be used with non-missing baseline and post-baseline WOMAC pain subscale, and other important covariates to impute any missing data including missed visits and missing data due to dropouts. The seed to be used is 20220420. The results from the MI will then be used to derive the value of the change from baseline in the WOMAC pain subscale score at each timepoint, and then analyzed using the analysis of covariance (ANCOVA) model. The results of the 100 analyses will be transformed into a normal statistic and combined into a single analysis using PROC MIANALYZE.

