5.3 Missing Data

WOMAC pain scores will be imputed as described in Section 4.9 for the primary analysis based on multiple imputations. All other analyses will be based on available data. Handling of plasma values that are below the limit of quantification with respect to the pharmacokinetic analyses are described in Section 4.16.1.

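### The WOMAC pain responder analyses drop every participant without a score at the visit, although the primary analysis already imputes that same score

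*SAP*

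**What the plan says.** **Responder endpoints.** SAP 4.12 sets the rule for all secondary endpoints: "Secondary endpoints will be analyzed based on the ITT Analysis Set using observed data only". The same paragraph names the 30% and 50% WOMAC pain responder endpoints at Weeks 5 and 17. It specifies a logistic model "with main effect treatment and covariates study center and baseline WOMAC pain subscale score". SAP 5.3, after referring to imputation for the primary analysis, adds: "All other analyses will be based on available data". SAP 4.1 sets the denominator: "Percentages will be calculated out of the number of participants in the given population with a non-missing result". Neither document gives a non-responder rule or an imputed responder analysis.

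**Primary endpoint.** SAP 4.9 imputes the WOMAC pain score 100 times and derives change from baseline at each timepoint: "All missing visits data will be imputed using all prior visits data as well as treatment". Data missing at random use the randomized arm, "whereas data that is missing due to treatment (adverse event, lack of efficacy) will be imputed using placebo as the treatment".

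**Early leavers.** Protocol 5.4.1 says the assessments for those who withdraw early "are as listed for FU/EOT Visit 11 and Safety Follow-up Phone Visit 12". Protocol 8.5.1 says the Visit 11 procedures "apply to Visit 11 and EOT visit for participants that have discontinued trial prior to completion of Visit 10 procedures and assessments". That list contains no WOMAC, and the Schedule of Events shows WOMAC after randomization only at Visits 6 and 10.

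**The concern.** The primary mean difference and the responder difference come from the same questionnaire, knee and visit, but they treat leavers differently. The primary analysis keeps all randomized participants and, after an adverse event or lack of efficacy, imputes as if on placebo. The responder analysis compares only those who supplied a score. A participant who leaves after Visit 6 has a Week 5 score, but the Week 17 responder model does not use it.

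The practical stake is dose selection. SAP 1.2 says the trial should establish the most suitable dose for Phase 3, and responder rates by dose are likely to be read for that purpose. If dropout differs by dose, the observed-only rates compare differently selected completers, and no planned analysis shows how much that matters.

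**Working it through.** **1. The plan's own figures.** No power or response rate is stated for the responder endpoints. The only related figures are the primary power values in SAP 4.3. With 15% dropout there are 104 × 0.85 = 88.4 evaluable per arm. A difference of 10, SD 19.2 and two-sided 0.0188 then give 86.7% power for one comparison (stated: 86% for the scenario with one effective arm). Simulating the equal-weight combination test reproduces all 12 cells to within 2 points. The 15% dropout input is therefore used below as the plan uses it.

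**2. How many participants are affected.** Lost by week t = 416 × 0.15 × t/T, where T is the period over which dropout is spread. The SAP says only that it is even over the study, so T is taken as 17, 20 or 30 weeks.

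| T (weeks) | Lost by Week 5 | Lost by Week 17 | Lost between |
|---|---|---|---|
| 17 | 18.4 | 62.4 | 44.0 |
| 20 | 15.6 | 53.0 | 37.4 |
| 30 | 10.4 | 35.4 | 25.0 |

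So about 35 to 62 of 416 (8.5% to 15%) have no Week 17 score, and about 25 to 44 of these left after Week 5. Participants who stay but miss Visit 10 come on top.

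**3. Hand check of the size.** Assume 50% responders on active and 35% on placebo (not document figures). If 15% of each arm is missing and active leavers respond at the placebo rate, the active rate is 0.85 × 50 + 0.15 × 35 = 47.75%. The difference is 12.75 points against 15 observed-only, a gap of 2.25 points. At 8.5% the gap is 0.085 × 15 = 1.3 points. This ignores the Week 5 score, which carries part of the treatment effect into the imputation and so shrinks the gap.

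**4. Simulation with the SAP 4.9 logic.** Assumptions:
- 600,000 per arm; bivariate normal response at Weeks 5 and 17, correlation 0.5 or 0.7; cut-off giving 50% versus 35%.
- All dropout placed after Week 5, either random or more likely in poor Week 5 responders (logistic, slope 1 per SD).
- Week 17 imputed by regression on Week 5 and treatment, with placebo as the treatment for adverse-event or lack-of-efficacy leavers and the randomized arm otherwise.

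The gap is the observed-only minus the imputed difference, in percentage points. For (a), all dropout due to adverse event or lack of efficacy and the Week 5 effect equal to Week 17 (correlation 0.5, then 0.7):

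| Dropout active/placebo | Random | Selective |
|---|---|---|
| 8.5% / 8.5% | 0.67, 0.40 | 0.79, 0.68 |
| 15% / 15% | 1.12, 0.71 | 1.40, 1.19 |
| 20% / 10% | 1.53, 0.93 | 3.29, 3.50 |
| 10% / 20% | 0.80, 0.47 | -0.58, -1.35 |

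(b) As (a) with half the effect at Week 5: +0.9 to +2.3 (random), -0.9 to +4.4 (selective). (c) Half of dropout for adverse event or lack of efficacy: +0.2 to +1.1 (random), -1.5 to +3.6 (selective).

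Across (a) to (c), equal dropout gives about 0.2 to 1.8 points. Gaps above about 2.4 need both the 20%/10% imbalance and selective loss. Negative gaps appear only with selective loss that is heavier on placebo. Those who leave before Week 5 have no Week 5 score, so their contribution lies nearer to the hand check in step 3.

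**5. Scale.** The standard error of 50% versus 35% with 88 per arm is sqrt(0.25/88 + 0.2275/88) = 7.4 points.

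**The case against.** The strongest reply is that observed-only is a legitimate, openly prespecified choice. Protocol 10.4.3 says that a wholly missing questionnaire is not imputed, and the SAP follows a natural reading of that for secondary endpoints. Nothing requires a secondary endpoint to share the primary missing-data strategy. Imputing and then dichotomising is also only one option. Counting leavers as non-responders would, on the same assumed rates, give differences of 12.75 points (15%/15% dropout), 8.5 points (20%/10%) or 17 points (10%/20%). The endpoint has no multiplicity control and no stated power.

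Much of this stands. A reader might infer that the SAP contradicts the protocol. It does not: protocol 10.4.6 sets the ITT set for secondary endpoints without saying how missing scores are handled. A reader might also infer that the loss would be hidden. It would not: protocol 10.4.1 and 10.4.6 call for n and number missing by visit and treatment group, and SAP 4.6 tabulates withdrawal reasons by arm.

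The objection does not answer the core. The model drops randomized participants from an analysis labelled ITT and leaves the Week 5 score of later leavers unused. It also handles leavers differently from the primary analysis of the same score, while datasets that resolve this are already to be produced.

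**Conclusion.** The point holds as a modest improvement to a secondary endpoint. What is missing is any responder analysis, main or sensitivity, that follows the primary missing-data strategy.

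On the plan's own assumption of even dropout with no stated imbalance, the likely effect is small: about 0.2 to 1.8 points, at most roughly a quarter of the standard error (1.8/7.4 = 0.24). The wider range of about -1.5 to +4.4 points rests on invented dropout imbalances of 20%/10% or 10%/20%. All these sizes depend on the assumed 50% and 35% responder rates and on placing all dropout after Week 5. The documents give neither responder rates nor dropout reasons.

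A reader might infer that observed-only always flatters the active arms. That was so in most scenarios, but the sign reverses when poor early responders leave more often on placebo, so no direction can be claimed in advance. Nor does the point reach the primary test, its alpha or its power.

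**What to change.** - **SAP 4.12 and 5.3:** derive 30% and 50% responder status, and the cumulative distribution, at Week 5 and Week 17 from the 100 datasets already imputed for the primary endpoint. Fit the planned logistic model in each dataset and combine with PROC MIANALYZE. Covering both visits avoids one endpoint following two rules.
- **Sensitivity:** keep the observed-only responder analysis, shown beside the planned per-arm n and number missing.
- **SAP section 6:** record that the protocol 10.4.3 sentence on wholly missing questionnaires is not applied to WOMAC pain responder status.

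Cost: minor programming and a short wording change, with no new data. The reported difference may come out slightly less favourable. Imputation can also count a leaver as a responder in some datasets, which the report should say plainly.
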